7. ADVERSE EVENTS

All AEs in this trial will be collected and processed in accordance with ICH-GCP and national and local laws and regulations. In line with these regulations, the investigator is responsible for reporting SAEs to Allucent, the sponsor's designee, within the appropriate timelines (see below). If required, the investigator is also responsible for notifying the appropriate local ethics committee of SAEs per the guidelines of the Institution and in accordance with aforementioned laws and regulations.

All AEs involving injection site reactions and dermatological reactions must be documented with color digital photography in addition to standard documentation methods.

7.1 Definitions

7.1.1 Adverse Event (AE)

An AE is defined as any untoward medical occurrence in a clinical trial subject administered with a medicinal product and which does not necessarily have a causal relationship with this treatment. An AE can therefore be any unfavourable and unintended sign (including an abnormal laboratory finding), symptom, or disease temporally associated with the use of an IMP, whether or not considered related to the IMP. All AEs reported by the subject or observed by the investigator or his staff will be recorded.

7.1.2 Treatment-Emergent Adverse Event (TEAE)

All AEs reported from the start of the trial (Day 1) are considered TEAEs.

7.1.3 Adverse Drug Reaction (ADR)

All noxious and unintended responses to the CyPep-1 and / or to the pembrolizumab medicinal product, related to any dose, should be considered as adverse drug reactions (ADRs). The phrase "responses to medicinal product" means that a causal relationship between the medicinal product and an AE is at least a reasonable possibility, i.e., a relationship cannot be ruled out. ADRs are also referred to as toxicity.

7.1.3.1 Tumor lysis syndrome (TLS)

A possible risk associated with CyPep-1 intratumoral administration, considering the mode of action of CyPep-1, or of pembrolizumab, is TLS, which needs to be mitigated, especially for the frail elderly patients. TLS can be mitigated by starting therapy at a low dose of CyPep-1 (as planned for the first cohort of subjects enrolled in Phase I of the trial), by slow dose ramp-up (as planned for cohorts in Phase I of the trial), and by staggered approach in Phase II combination arm (initial dosing of 3 subjects at RP2D in combination with pembrolizumab before enrolling all subjects) and by appropriate preventive measures. Measures to prevent TLS include TLS risk assessment, prophylactic hydration and medication prior to initial dosing with careful monitoring during the first 4 hours after dosing for metabolic or clinical signs of impending TLS, according to institutional standards.

To ensure prophylactic hydration, subjects should consume ≥ 2 L of fluid intake per day, starting ≥ 48 hours prior to first dose/each dose escalation and for ≥ 24 hours thereafter. For patients who have difficulty to maintain adequate oral hydration, intravenous hydration is recommended, at an infusion rate of 150-200 mL/hr (i.e., 2-3 L per day) for initial dosing; for following dose escalations, an intravenous hydration with 1.5-2 L per day is advisable.

Prophylactic medications for TLS include uric acid reducers such as allopurinol (300 mg orally daily, starting ≥ 72 hours prior to first dose and continued for ≥ 1 week after the last dose escalation).

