during or after IT administration, it is recommended to provide celecoxib 400 mg as premedication every 6 hours for 24-48 hours. Premedication should be administered for subsequent CyPep-1 doses based upon clinical judgment and presence/severity of prior reactions. This regimen may be modified based on local treatment standards and guidelines as appropriate. To ensure prophylactic hydration, subjects should consume ≥ 2 L of fluid intake per day, starting ≥ 48 hours prior to first dose/each dose escalation and for ≥ 24 hours thereafter. For subjects who have difficulty to maintain adequate oral hydration, intravenous hydration is recommended, at an infusion rate of 150-200 mL/hr (i.e., $2\text{-}3$ L per day) for initial dosing; for following dose escalations, an intravenous hydration with 1.5-2 L per day is advisable. For lesions > 7 cm, weekly CyPep-1 administration should be considered by the Investigator for the first 6 weeks, on Days 1, 8, 15, 22, 29 and 36 of cycle 1. The assessments are as per scheduled visit for Day 1, 15 and 29. Visits on Day 8 and 22 will follow the assessments as per D15 (C1V2) with the exclusion of central lab sampling for cytokine analysis and blood sampling for immune cell phenotyping. For Day 36 assessments as specified in the schedule need to be performed, with additional assessments: Pre-dose ECG, Vital Signs PRE- & 15m, 30m, 1h, 2h, 4h POST-dose, Coagulation and Pregnancy test (if applicable).

20. All concomitant medication/procedures should be reported beginning upon ICF signature until FU (or EoT, if it occurs more than 30 days after the last CyPep-1 or pembrolizumab administration).

21. Reporting period is from ICF signature until FU (or EoT, if it occurs more than 30 days after the last CyPep-1 or pembrolizumab administration). After the FU visit (or EoT, if it occurs more than 30 days after the last CyPep-1 or pembrolizumab administration), only ongoing (S)AEs related to CyPep-1 or pembrolizumab administration will be collected. Adverse events will be assessed using CTCAE v5.0 including start and stop dates, severity, relationship to CyPep-1 or pembrolizumab, outcome and action taken.

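### The IV hydration rate of 150-200 mL/hr and its stated equivalent of 2-3 L per day agree only if the infusion runs about 13.3-15 hours a day, and no infusion hours are given

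*Protocol*

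**What the plan says.** Protocol Section 7.1.3.1 sets out hydration as a preventive measure against tumor lysis syndrome. The default is oral intake, continued for at least a day after the dose: "subjects should consume ≥ 2 L of fluid intake per day, starting ≥ 48 hours prior to first dose/each dose escalation and for ≥ 24" (the last figure is in hours).

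For those who have difficulty maintaining oral hydration, the section says that "intravenous hydration is recommended, at an infusion rate of 150-200 mL/hr (i.e., 2-3 L per day) for initial dosing". A lower volume, without a rate, follows for later steps: "for following dose escalations, an intravenous hydration with 1.5-2 L per day is advisable".

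Footnote 19 to the Schedule of Assessments carries the same instruction ("intravenous hydration is recommended, at an infusion rate of 150-200 mL/hr"), with the same 2-3 L per day in brackets. Neither place gives infusion hours per day, a stopping point or a maximum daily volume. SAP Section 9.5.4 says only that prophylactic hydration data will be listed for the safety analysis set.

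**The concern.** The abbreviation i.e. tells the reader that the rate and the daily volume are the same quantity in two units. As a plain conversion of mL per hour to litres per day, they are not. A site that sets the pump by the rate and leaves it running gives one volume. A site that stops at the stated volume gives another. Both can say that they followed the protocol.

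The clause is the one that applies to an individual subject. Every subject has an initial dose, and the alternative IV figure is tied to dose escalations, whereas Section 3.1 and the synopsis rule out escalation within a subject. Because footnote 19 repeats both figures, a site that checks the second place finds no clarification. At stake is the consistency of a safety instruction across sites, not the design or the statistical analysis.

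**Working it through.** **Inputs**, all from Protocol Section 7.1.3.1 and repeated in footnote 19: rate 150-200 mL/hr; stated daily volume 2-3 L. Infusion hours per day: not stated.

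**Step 1. Try to reproduce the stated volume.** Daily volume (L) = rate (mL/hr) × hours ÷ 1000. With 24 hours, which is an assumption:

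- 150 × 24 ÷ 1000 = 3.6 L
- 200 × 24 ÷ 1000 = 4.8 L

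The stated 2-3 L is not reproduced, and the two ranges do not overlap.

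**Step 2. Run the conversion backwards.** Spread over 24 hours:

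- 2000 ÷ 24 = 83 mL/hr
- 3000 ÷ 24 = 125 mL/hr

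This range does not overlap 150-200 mL/hr either, so rounding does not explain the gap.

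**Step 3. Size of the gap under the 24-hour assumption, low end against low end and high end against high end.**

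- Low ends: 3.6 ÷ 2 = 1.8-fold, a difference of 3.6 − 2 = 1.6 L per day
- High ends: 4.8 ÷ 3 = 1.6-fold, a difference of 4.8 − 3 = 1.8 L per day

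**Step 4. Infusion hours that make the figures agree.** Hours = volume ÷ rate:

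| Rate | Hours for 2 L | Hours for 3 L |
|---|---|---|
| 150 mL/hr | 13.3 | 20 |
| 200 mL/hr | 10 | 15 |

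For the whole rate range to fall within 2-3 L, the lower rate must reach at least 2 L (13.3 hours or more) and the higher rate must not exceed 3 L (15 hours or less). The window is therefore about 13.3-15 hours a day. As a check, 14 hours gives 150 × 14 ÷ 1000 = 2.1 L to 200 × 14 ÷ 1000 = 2.8 L. No such limit appears in either place.

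**The case against.** The strongest reply is that the two figures need not conflict: run the infusion at 150-200 mL/hr until 2-3 L has been given, then stop. Step 4 shows that this is feasible, and no text prescribes a 24-hour infusion. This stands, and it is why 3.6-4.8 L has to be labelled as resting on an assumption. It does not remove the problem, because the reader has to supply the infusion hours or the stopping rule.

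The scope is also narrow. IV hydration is recommended rather than required, and only for subjects who struggle with oral intake. The documents do not say how many that will be.

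Several stronger readings are tempting, and the documents do not support them:

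- **A 1.2- to 2.4-fold discrepancy.** These figures come from crossing opposite ends of the ranges (3.6 ÷ 3 and 4.8 ÷ 2). They are arithmetically possible extremes, but matched ends are the fair comparison.
- **Excess fluid on each of at least three days.** The window of 48 hours before and 24 hours after is attached to oral intake. The IV sentence says only that it concerns initial dosing.
- **Particular danger to frail elderly patients.** Section 7.1.3.1 names that group for tumor lysis risk, not for fluid overload.
- **Contamination of the primary safety endpoint.** Events before the first dose are not treatment-emergent and are summarised separately (Protocol Section 8.1.3; SAP Section 11.1.3 and Appendix 1). For events after dosing, the causality assessment must weigh alternative explanations (Protocol Section 7.2.2.2), and the SAP tabulates related events separately. Nothing in the documents shows that this line would shift adverse event, DLT or TLT counts or the recommended dose.

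Finally, the benefit of a correction is smaller than it would have been at the start: Phase I was completed in August 2021, and the footnote to SAP Section 6.1 reports that Arm D stopped recruiting after one subject.

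**Conclusion.** The point holds as a numerical inconsistency in a safety instruction, present in two places. Assuming a continuous 24-hour infusion, the rate gives 3.6-4.8 L per day against a stated 2-3 L, or 1.6- to 1.8-fold at matched ends. Under a daily infusion of about 13.3-15 hours the two figures are compatible. The missing infusion hours decide which case applies, and the protocol does not give them.

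The line should be corrected because it bears on patient safety and allows sites to differ while complying. It does not threaten the design, sample size or planned analyses. The finding is not that any subject received too much fluid, and no effect on the primary endpoint is claimed.

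**What to change.** Ask the clinical team to reconcile three items in Section 7.1.3.1 and footnote 19: the infusion rate, the daily volume and the infusion hours per day. The text should make clear which of them governs, and both places should carry identical wording. The choice of figures is a clinical decision on which this review takes no position.

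The edit is one line in two places. It still has to go through the amendment procedure in Protocol Section 10.6, with ethics committee and authority approval if the change is classed as substantial, so it could be carried with another amendment. No change to the SAP is needed.

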7.1.4 Unexpected Adverse Drug Reaction

An unexpected adverse drug reaction is an adverse drug reaction of which the nature or severity is not consistent with the available product information, e.g. the IB for an unapproved investigational product. ADRs that are more specific or more severe than described in the investigator's brochure should also be considered unexpected.

7.1.5 Serious Adverse Event (SAE)

Any untoward medicinal occurrence or effect that at any dose:

- Results in death (not due to disease progression);
- Is life-threatening (the subject was at risk of death at the time of the event; it does not refer to an event that hypothetically might have caused death if it were more severe);
- Requires hospitalization or prolongation of existing hospitalization;
- Results in persistent or significant disability or incapacity;
- Is a congenital anomaly or birth defect.

The following are not considered (and do not need to be reported) as SAEs:

- Hospitalization due to a social indication
- Elective pre-planned hospitalizations for treatment of an existing condition prior to entering the trial
- Hospitalizations due to tumor-related symptoms or tumor progression

Any event that does not meet the above criteria may also be considered by the investigator to be a SAE, based on appropriate medical and scientific judgment. This includes important medical events that may not be immediately life-threatening or result in death or hospitalization but may jeopardize the subject or may require intervention to prevent one of the other outcomes listed in the definition above. For example, allergic bronchospasm requiring intensive treatment in an emergency room or at home; convulsions that may not result in hospitalization; development of drug abuse or drug dependency.

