CyPep-1 has been shown to selectively target tumor cell membranes based on their altered molecular composition, which in turn leads to lysis of tumor cells by removal of the cell membrane.

Figure 1. Mode of action of CyPep-1.

This mode of action of CyPep-1 induces tumor cell death resulting in the release of tumor antigens, and potentially induces a tumor-specific immune response by in-situ immunization (Figure 1).

Preclinical toxicology studies have shown a favorable safety profile and potent anti-tumor activity of CyPep-1 in several tumor models. CyPep-1 was shown to modulate the tumor microenvironment by increasing the presence of CD8+ T-cells and by potentiating the effects of immune checkpoint inhibitors (ICIs; please see Investigator Brochure). As such, we hypothesize that intratumoral (IT) injection with CyPep-1 leads to transformation of immunological “cold” and ICI treatment-resistant tumors into “hot” and immunological active tumors that can be successfully treated with immune-modulating agents.

TRIAL RATIONALE:

Treatment with ICIs has been shown to result in long lasting anti-tumor responses in selective patients with different tumor indications. However, only a subset of these patients obtains durable remission. Studies have indicated the presence of intratumoral CD8+ T-cells to be a positive predictive factor for response to ICI therapy. Thus, treatment strategies that aim at recruiting tumor antagonizing cellular components of the immune system hold great promise and are currently a main focus in oncology research.

Current evidence revealed an association between tumor mutational burden and tumor immunogenicity. In order to proliferate, antigenic tumors develop mechanisms that enable them to evade immune-mediated destruction through a process termed immunoediting. However, while mutational load represents a predictive factor for ICI response, its predictive power seems modest; rather, ICI efficacy may be associated with the presence of specific neoantigen-generating mutations. This observation suggests that a qualitative neoantigen-directed immunotherapy holds great potential. New therapeutic modalities in this category should ideally meet two critical criteria: 1) exposing tumor specific antigens, and 2) inducing an inflamed tumor microenvironment. Furthermore, the capacity of such therapeutic modalities may result in an extended patient population of responders and potentially increase the overall efficacy of ICIs.

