The dose of pembrolizumab in combination with CyPep-1 in the combination arm will be 400 mg Q6W. Dosing of CyPep-1 will be aligned such that subjects will receive both pembrolizumab and the first dose of CyPep-1 on the same day (C1V1). After C1V1, pembrolizumab dosing will continue following a Q6W dosing scheme until 18 cycles, confirmed PD, unacceptable toxicity or consent withdrawal.

DOSE-MODIFICATION CRITERIA:

CyPep-1: No major toxicity is expected. There may be minor local toxicity or tumor ulceration due to the treatment procedure, which can be treated according to Standard of Care.

In case of toxicity, the administration of CyPep-1 may be delayed at the discretion of the investigator and is to be discussed with the medical monitor. Neither a dose reduction, nor intra-subject dose escalation of CyPep-1 is allowed.

Dose modification of pembrolizumab in Arm B will be according to the provided dose modification and toxicity management guidelines (refer to Section 5.3.6).

SAFETY ASSESSMENTS:

Safety will be assessed by means of physical examinations, body weight, vital signs, ECOG performance status, laboratory evaluations (hematology, biochemistry, coagulation, urinalysis), electrocardiograms (ECG), and recording of concurrent illness/therapy and adverse events (as defined by CTCAE v5.0). All assessments will be performed as indicated in the Schedule of Assessments ([SoA, Table 1](#)). Additional assessments may be performed as clinically indicated.

EFFICACY ASSESSMENTS:

Clinical efficacy of CyPep-1 monotherapy (Phase I dose escalation and Phase IIa Arms A, C, and D) and in combination with pembrolizumab (Phase IIa Arm B) will be measured by radiologic assessments (i.e., caliper, CT, MRI) every 8 weeks, starting from C1V1 for all phases and arms as baseline. The imaging modality must be the same for all efficacy measurements.

Radiologic assessments will be evaluated based on the investigator's assessments at the clinical sites according to the consensus guideline iRECIST ([Appendix D](#), based on modified

RECIST) and response (iCPD, iUPD, iSD, iPR, iCR) will be defined taking into account the total disease burden (as required per iRECIST using modified RECIST).

ORR in injected and non-injected lesions per itRECIST will be estimated by statistical programming using data collected from iRECIST assessments.

The following tumor lesion(s) will be followed-up for efficacy:

- One or more injected lesion(s) that are treated with CyPep-1 injection.

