4. SELECTION OF TRIAL POPULATION

4.1 Inclusion Criteria

For Phase I and Phase IIa Arms A and C:

1. Histologically or cytologically confirmed locally advanced (unresectable) or metastatic tumors (solid tumor or lymphoma) with an accessible tumor lesion for intratumoral injection of CyPep-1 malignancy (including lymphomas) that is either:
 - a. Refractory to standard-of-care treatment
 - b. Have a disease for which there is no standard therapy considered appropriate. Metastatic deposits (including cutaneous/subcutaneous lesions and metastatic deposits in lymph nodes) of tumors for which IT injections may be performed are eligible. Pure cutaneous infiltrations (e.g., breast cancer cutaneous carcinomatosis) are ineligible.
2. 1 to 3 non-ulcerated transcutaneously accessible lesion(s) for injection and measurable as defined by iRECIST. All other tumor lesion(s) may be selected for efficacy follow-up, but will not be subjected to treatment with CyPep-1.
3. Presence of tumor lesion(s) (that have not been previously irradiated) suitable for biopsy at screening and at Week 6.

For Arm C:

4. Confirmation of the presence of at least one liver metastasis by imaging.
5. Subjects must have measurable disease which is equal to one or more metastatic liver lesions that can be accurately and serially measured; that are greater than 1 cm dimension and for which the longest diameter is greater or equal to 1 cm as measured by CT (computed tomography) scan or magnetic resonance imaging (MRI). The metastatic liver lesion(s) must not be in an area that received prior localized therapies.
6. Metastatic liver lesion(s) for injection with >50% radiological visible necrosis must be avoided and the lesion must be located where any tumor swelling will not lead to gall bladder tract obstruction or lead to bleeding risk.

For Arm D:

7. Histologically or cytologically confirmed diagnosis of advanced (unresectable Stage III) or metastatic (Stage IV: M1a and/or M1b) melanoma considered incurable by the standard of care. For metastatic melanoma, only cutaneous, subcutaneous, lymph node, or lung metastases are allowed.
8. Previously exposed to ICI(s) and be categorized following the SITC Immunotherapy Resistance Taskforce ([Kluger 2020](#)) meeting one of the following:
 - a. Have primary resistance: PD-(L)-1 inhibitor exposure ≥6 weeks and have the best response as one of the following:
 - i. PD,
 - ii. SD for <6 months.

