7.1.6 Suspected Unexpected Serious Adverse Reaction (SUSAR)

SUSARs are SAEs that are at a minimum possibly related to the study agent and are unexpected (i.e., not listed in the investigator brochure). SUSARs will be collected and expeditiously reported to CAs and IECs according to applicable regulatory requirements.

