7.2.3 Reporting of SAEs

Information on SAEs will be collected from the time of ICF signature until the FU visit (or until EoT, if it occurs more than 30 days after the last CyPep-1 or pembrolizumab administration). After the FU visit (or EoT visit, if it occurs more than 30 days after the last CyPep-1 or pembrolizumab administration), only ongoing AEs or SAEs related to CyPep-1 and / or pembrolizumab administration will be collected.

Specific timing for Arm B is provided in [Section 7.2.1.3](#).

All AEs that meet the criteria for SAE require the completion of a trial specific SAE Form (or Additional Safety Information [ASI] Form), including an assessment of the relationship to the trial drug. This applies to all SAEs, whether or not they were considered to be related to the trial treatment.

The investigator must report all SAEs to [REDACTED] immediately, i.e. within 24 hours (by fax or e-mail) of learning of its occurrence. For this reporting, a SAE Form (provided in the investigator File) needs to be completed in English. The original SAE report form, together with the fax confirmation sheet (if applicable) or e-mail, must be kept at the study site. Follow-up information about a previously reported SAE must also be reported to [REDACTED] within 24 hours of receiving the information. This follow-up data must be provided on an ASI Form or an updated SAE form. The SAE report should provide a detailed description of the AE and should include anonymized copies of hospital records and other relevant documents. Autopsy results, if applicable, should also be sent to [REDACTED] as soon as they become available. Copies of each report will be kept in the investigator File.

All SAEs will need to be followed actively until resolution or stabilization. The above is also applicable to follow-up SAE information.

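### The SAE definition exempts hospitalisations for tumour-related symptoms without a relatedness condition, so a hospitalisation caused by injecting a tumour can escape SAE reporting

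*Protocol*

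**What the plan says.** Protocol 7.1.5 makes hospitalisation, new or prolonged, one of the criteria for an SAE. It then gives a list of exceptions under the words "The following are not considered (and do not need to be reported) as SAEs". The third exception is "Hospitalizations due to tumor-related symptoms or tumor progression". SAP 11.1 carries the same list. In neither place is the exception tied to the causality assessment, the injected lesion or the procedure.

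On the drug, the protocol synopsis (Trial Background) says that CyPep-1 targets tumour cell membranes, "which in turn leads to lysis of tumor cells by removal of the cell membrane". The synopsis section on dose-modification criteria says "There may be minor local toxicity or tumor ulceration due to the treatment procedure". Protocol 7.1.3.1 introduces tumour lysis syndrome as "A possible risk associated with CyPep-1 intratumoral administration".

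On what follows from SAE status, Protocol 7.2.3 requires a report within 24 hours and adds: "This applies to all SAEs, whether or not they were considered to be related to the trial treatment". Protocol 7.1.6 states that "SUSARs are SAEs that are at a minimum possibly related to the study agent and are unexpected". SAP 11.1.3 gives serious treatment-emergent events their own lines in the overview table and their own tables by system organ class and preferred term.

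**The concern.** Here the injection site is the tumour. Pain, swelling, bleeding or ulceration of an injected lesion may be a drug reaction, an effect of the needle, or the disease. An investigator who records the reason for admission as a tumour symptom can apply the exception without first asking whether treatment contributed, and two sites could classify the same admission differently.

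Safety and tolerability of intratumoral administration is the first primary objective (Protocol 2.1.1) of an open-label, first-in-human trial. Serious local events in injected lesions bear directly on that objective, and this exception operates at exactly that point.

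**Working it through.** The question is one of definitions, so the check sets the relevant sections side by side. The plan gives no figure to reproduce.

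**1. Is there a relatedness condition anywhere?** Protocol 7.1.5 and SAP 11.1 have none. Protocol 7.2.2.2 defines a five-level causality scale, reduced to related or unrelated at analysis, but nothing links that scale to the exception.

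**2. Can a treatment effect be read as a tumour symptom?** Yes.
- The mechanism is lysis of the tumour, and the protocol expects local toxicity or ulceration of the tumour from the procedure.
- SAP 11.1.3 pools two preferred terms for pain from the tumour, and separately provides for injection site reactions that were reported inconsistently. Coding at this boundary is thus already known to vary.
- On the progression half of the exception, Protocol Appendix D says that tumour flare can appear as any of the changes that count as radiographic progression.

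**3. What does the event lose if the exception is applied?**
- The 24-hour report (7.2.3), because that duty attaches to SAEs.
- SUSAR assessment (7.1.6), because a SUSAR must first be an SAE.
- The serious-event lines and tables in SAP 11.1.3. The SAP rule that a missing seriousness assessment counts as serious does not help, since seriousness would be recorded as no.
- Late collection in Arm B. Under Protocol 7.2.1.3, AEs are reported through 30 days after treatment stops. Those meeting serious criteria are reported through 90 days, or 30 if new anticancer therapy starts. The later catch-all covers only drug-related SAEs. An event starting on days 31 to 90 that is denied SAE status may therefore be collected nowhere.
- Late follow-up generally. Protocol 4.3.1 extends reporting to at least 3 months after the last injection for subjects who leave active follow-up, but only for SAEs.

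**4. What still catches it?**
- The life-threatening and disability criteria in 7.1.5 remain.
- An investigator may choose to call any event an SAE. This is optional.
- AEs are recorded regardless of causality (7.2.2), except those resulting from relapse or progression, which that section says are not AEs.
- Hospitalisation is part of the general description of Grade 3 (Appendix C), and SAP 11.1.3 tabulates and lists Grade 3 or higher events.
- DLTs and TLTs (3.1.2) depend on grade and relatedness, not on SAE status. Their window is Cycle 1, apart from a judgement-based DLT item without a time limit, while treatment continues until confirmed progression. Arm D has no formal DLT period, though SAP 6.1 notes that it stopped after one subject.
- Events of Clinical Interest (7.2.1.1, Arm B) are overdose and a liver-test pattern, so they do not cover local events in general.

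None of these makes SAE reporting mandatory for a possibly related admission classed as tumour-related.

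**5. Can the size be computed?** No. The documents give neither a rate of admission for tumour symptoms nor the share caused by treatment. All that follows is the weight of one subject in an incidence:
- Arm B: 1/15 = 6.7 percentage points.
- Monotherapy at the RP2D: 6 + 9 = 15 subjects, again 6.7 points. If Arm A expands, 6 + 18 = 24 and 1/24 = 4.2 points.

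These figures describe small denominators. They do not estimate how many events are missed.

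**The case against.** The best counter-argument is that the exception already speaks of admissions caused by the tumour. On that reading, an event judged related to CyPep-1 falls outside it. Protocol 7.1.3 supports this: any noxious response with at least a reasonable possibility of drug causation is an adverse drug reaction, also called toxicity, and tumour lysis syndrome sits under that heading. Local effects are also handled as AEs in practice. Section 7 requires photographs of injection site reactions, and 5.3.4 reports 12 related Grade 1 and 2 injection site pain events at 5 mg/mL. This reading is reasonable, but 7.1.5 does not state it, and for a drug acting inside the tumour the two causes are hard to separate at the bedside.

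Four stronger readings are tempting and are not supported:
- That the rule expressly exempts related events. It does not; it is silent, and the silence is the defect.
- That such events vanish from committee review. Protocol 3.1.1 has the Dose Escalation Committee review safety data, and in Phase IIa weigh severity and relatedness of safety events. Neither depends on SAE status.
- That the protocol predicts serious swelling, obstruction or bleeding. The Arm C criterion that "the lesion must be located where any tumor swelling will not lead to gall bladder tract obstruction or lead to bleeding risk" is an eligibility safeguard which keeps such lesions out. The synopsis expects no major toxicity.
- That the absence of related SAEs in Phase I (1.6.1, 5.3.4) results from this exception. Nothing in the documents shows that.

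It is also fair to say that a change now comes late. Phase I ended in August 2021, a mid-study analysis was done in summer 2023, and the SAP is dated June 2024. New wording will not by itself reclassify recorded events, so the fix needs a re-review.

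**Conclusion.** The point stands in a limited form. As written, the exception can keep a non-life-threatening hospitalisation that treatment may have caused out of 24-hour reporting, SUSAR assessment and the serious-event tables, and in Arm B possibly out of collection after day 30. Events recorded as AEs remain in the AE and Grade 3 or higher tables, in DLT or TLT assessment where the window applies, and within the committee's view.

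The conclusion assumes that some investigators would class symptoms of an injected lesion as tumour-related. The text permits this, but the documents do not show how often it happens, so the number of events affected cannot be derived. The defect changes no sample size, decision threshold or confidence bound. It is worth correcting because it touches a primary objective and the correction is small.

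**What to change.** - In Protocol 7.1.5 and SAP 11.1, limit the exception to hospitalisations assessed as not related or unlikely related, on the scale in 7.2.2.2, to CyPep-1, the injection procedure or pembrolizumab. Name the procedure explicitly, because that scale refers only to the two drugs.
- Put the same condition on the sentence in Protocol 7.2.2 that removes events resulting from relapse or progression from AE status. Otherwise an event could still drop out one level earlier.
- Before the Data Review Meeting (SAP 7.1), re-review recorded hospitalisations involving an injected lesion and settle their seriousness and relatedness under the new wording. Protocol Table 5 and 7.2.1 have hospitalisations asked about at every visit, so there is a source to work from.

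The cost is a protocol amendment with the submissions described in Protocol 10.6 and 11.1, a SAP revision, a limited re-review and a few more SAE reports.
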